## 8.2. General Approach/Considerations

The final analysis will be performed when all data has been retrieved, entered, cleaned, locked and frozen. Descriptive statistics for demographic and baseline characteristics will be summarized for all enrolled subjects. For categorical variables, the number and percentage of subjects in each category will be summarized. Continuous variables will be summarized by n, mean, standard deviation, median, Q1 (25% percentile), Q3 (75% percentile), minimum and maximum values.

## 8.3. Analysis of Key Study Endpoints

The primary endpoint is overall response rate (ORR). The ORR will be evaluated along with the exact 95% confidence interval. Secondary endpoints include platelet response, durable platelet response, transformation to AML, incidence of bone marrow fibrosis, and time-to-event outcomes such as progression-free survival (PFS) and overall survival (OS). The probabilities of PFS and OS will be estimated using the method of Kaplan and Meier. The incidence rates of other binary secondary endpoints will be estimated, along with the exact 95% confidence intervals. Subjects that discontinue the study prior to having achieved a clinical response will be considered to have not had an event.

**Patients receiving growth factors other than eltrombopag (erythropoietin, GM-CSF or G-CSF) will not be considered in the HI analysis for the time periods specified in Section 4.5.3 Supportive Care Guidelines. Hemoglobin levels and platelet counts collected from patients that have received a transfusion within the last 7 days will not be considered in the analysis.**

Survival or times to failure and time to progression functions will be estimated using the Kaplan-Meier method. The two-sided log-rank test will be used to assess the differences of time to events between groups.

The total number of dose administrations, the average dose (mg), and the cumulative dose administered will be summarized by eltrombopag treatment group.

Blood chemistry and complete blood counts will be summarized by treatment group at each time point.

Additional exploratory analyses of the key study endpoints will be performed as deemed appropriate.

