#### **6.2.3. Secondary Efficacy Endpoints**

The key secondary endpoints for this study are:

- To evaluate the safety and tolerability of the combination of eltrombopag and decitabine. Safety will be assessed by the overall incidence and severity of all study-treatment related adverse events per CTCAE v 4.0
- To evaluate the incidence of dose reductions and delays of decitabine therapy
- To evaluate the effect of eltrombopag on medically significant hemorrhagic events (defined as Grade 3 or 4 hemorrhagic events on CTCAE v 4.0)
- To evaluate the effect of eltrombopag on platelet and RBC transfusion independence per IWG-2006 criteria
  - o Platelet IWG-2006: A complete response is defined as a platelet count  $> 100 \times 10^9/L$ ; and a major response defined as an increase of platelet count by higher than  $30 \times 10^9/L$ .
  - o Durable platelet count: in which a hematologic improvement in platelets (HI-P) defined as either an increase  $\geq 30 \times 10^9/L$  from patients with a baseline platelet count  $\geq 20 \times 10^9/L$ , or an increase from  $< 20 \times 10^9/L$  to  $\geq 20 \times 10^9/L$  and by at least 100%, present for  $\geq 8$  weeks.
- Incidence of transformation to AML per FAB criteria ( $>30\%$  blasts) during treatment period and follow-up
- Incidence and severity of bone marrow fibrosis during treatment period and follow-up
- To examine the relationship between clinical response with ferritin level and other markers of iron burden at study start

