## 8. Statistical Considerations

This is an open label, phase II clinical trial to evaluate the efficacy of eltrombopag in combination with decitabine as a frontline therapy in patients with Intermediate-2 or High-Risk Myelodysplastic Syndrome (MDS). A total of 40 patients will be accrued from M.D. Anderson Cancer Center (MDACC), at a rate of 2-3 patients per month.

The primary endpoint is the overall response rate (ORR) based on the IWG-2006 criteria, which includes complete remission (CR), partial remission (PR), and hematologic improvement (HI). Patients' overall response will be assessed during the first four 28-day cycles of treatment. Patients who drop off the study early due to treatment-related toxicities will be counted as treatment failures (i.e., non-responders).

The method of Thall, Simon and Estey [1995] will be used for futility and toxicity monitoring for this study. The target overall response rate is 60% and the following futility stopping rule will be applied in cohort size of 10, starting from the 10th patient:  $\text{prob}\{p(\text{ORR}) < 0.6\} > 0.95$ , where  $p(\text{ORR})$  denotes the overall response rate. That is, the trial will be stopped early due to futility, if during the study we determine that there is more than 95% chance that the ORR is less than 60%. Assuming that the prior distribution of  $p(\text{ORR})$  is beta (1.2, 0.8), the stopping boundaries corresponding to this futility monitoring rule are shown below in Table 1. The operating characteristics (OCs) for this futility stopping rule are summarized in Table 2. The design software Multic Lean Desktop (version 1.2.0) developed by the Department of Biostatistics at M. D. Anderson Cancer Center (MDACC) was used to generate the futility stopping boundaries and the

OC table. In order to utilize the software for the design, a highly informative beta (600, 400) prior was assumed to approximate the target 60% overall response rate.

Table 1. Futility stopping boundaries in cohort size of 10.

Number of patients	Stop the trial if there are this many patients achieving overall response
10	0-3
20	0-8
30	0-13

Table 2. Operating characteristics for futility monitoring in cohort size of 10 (max sample size = 40).

True ORR	Prob(stop the trial early due to futility)	Average sample size
0.3	0.971	14.8
0.4	0.775	22.0
0.5	0.391	31.3
0.6	0.105	37.5
0.7	0.015	39.6

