## 8.1 Analysis Plan

The primary endpoint is overall response rate (ORR). The ORR will be estimated along with the exact 95% confidence interval. Secondary endpoints include incidence of dose reductions and delays of decitabine therapy, hemorrhagic events (defined as Grade 3 or 4 hemorrhagic events on CTCAE v 4.0), platelet and RBC transfusion independence per IWG-2006 criteria, transformation from MDS to AML, Incidence and severity of bone marrow fibrosis. Descriptive statistics will be used to summarize all secondary endpoints. The incidence rates of binary secondary endpoints will be estimated, along with the exact 95% confidence intervals.

The probabilities of time-to-event outcomes (such as time to transformation from MDS to AML and time to developing BM fibrosis) will be estimated using the method of

Kaplan and Meier. Log-rank tests will be used to compare the time-to-event outcomes among subgroups of patients.

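### AML transformation and marrow fibrosis are given both a crude proportion and a Kaplan-Meier estimate, and the plan does not say which is the main one or how early loss and death are handled

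*Combined protocol and SAP*

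**What the plan says.** Section 6.2.3 defines the fibrosis endpoint as "Incidence and severity of bone marrow fibrosis during treatment period and follow-up". AML transformation is defined over the same window. No duration is attached to either.

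Section 8.1 lists both among the secondary endpoints ("transformation from MDS to AML, Incidence and severity of bone marrow fibrosis") and states "The incidence rates of binary secondary endpoints will be estimated, along with the exact 95% confidence intervals". The next paragraph says "The probabilities of time-to-event outcomes (such as time to transformation from MDS to AML and time to developing BM fibrosis) will be estimated" by the Kaplan-Meier method. Section 8.1 therefore provides for both a proportion and a curve.

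Section 8.3 lists "transformation to AML, incidence of bone marrow fibrosis, and time-to-event outcomes such as progression-free survival (PFS) and overall survival (OS". It assigns Kaplan-Meier to PFS and OS by name and then says "The incidence rates of other binary secondary endpoints will be estimated, along with the exact 95% confidence intervals". Read naturally, AML and fibrosis fall in that binary group. Section 8.3 neither repeats nor withdraws the Kaplan-Meier analysis from 8.1. Its next sentence treats anyone who leaves the study before responding as not having had an event, and does not say to which endpoints this applies.

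Neither section names the main estimate, a time point, a censoring rule, or the treatment of death without the event.

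**The concern.** A binomial proportion estimates the risk by a given time only if every event-free patient was observed, or had died, by that time. The protocol does not arrange this. Section 4.2 lets patients stop for progression, toxicity, possible transplant, withdrawal or lack of benefit after 4 cycles. It also lets them continue to 12 cycles, with further treatment possible. The last scheduled visit comes 28 days after the last eltrombopag dose. A patient seen for two months without AML then counts the same as one seen for twelve.

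Section 2.3.2 states that eltrombopag may increase reticulin deposition and that a risk of clinically consequential fibrosis has not been excluded. An estimate that falls as patients leave sooner errs in the reassuring direction. Two analysts could follow the plan and report different risks from the same data.

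**Working it through.** The plan gives no expected rate, dropout or follow-up time for either endpoint, so there is no figure of its own to reproduce. What follows is an illustration.

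**Inputs from the documents.** n = 40 (Section 8: "A total of 40 patients will be accrued from M.D. Anderson Cancer Center (MDACC), at a rate of 2-3 patients per month"). Twelve 28-day cycles without delay take 12 × 28 = 336 days. With the 28-day safety visit, scheduled observation ends at about 336 + 28 = 364 days.

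**Assumptions.** The horizon T is 12 months. Hazards are constant and independent: e for the event, d for death without it, c for event-free loss. Each 12-month figure below is a net risk p, so hazard × T = -ln(1 - p).

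**Formulas.**
- Crude proportion expected = e/(e+d+c) × [1 - exp(-(e+d+c)T)]
- Cumulative incidence, death competing = e/(e+d) × [1 - exp(-(e+d)T)]
- Kaplan-Meier with deaths censored = 1 - exp(-eT)

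**Worked case: 20% risk, no deaths, 40% loss.** eT = 0.2231 and cT = 0.5108. Crude = 0.2231/0.7340 × (1 - 0.8 × 0.6) = 0.304 × 0.52 = 15.8%, against a true 20.0%.

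| Event-free loss by 12 months | Crude, no deaths (true 20.0%) | Shortfall, points | Events expected in 40 | Crude, 40% deaths (true 15.8%) |
|---|---|---|---|---|
| 0% | 20.0% | 0 | 8.0 | 15.8% |
| 20% | 18.0% | 2.0 | 7.2 | 14.4% |
| 40% | 15.8% | 4.2 | 6.3 | 12.8% |
| 60% | 13.3% | 6.7 | 5.3 | 10.9% |

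With 40% loss and no deaths, the shortfall is 2.1 points at a 10% risk and 6.2 points at a 30% risk.

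Deaths alone do not bias the crude proportion: with 40% deaths and no loss it equals the cumulative incidence, 15.8%. Kaplan-Meier with those deaths censored gives 20.0%, which is 4.2 points too high.

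**Sampling error.** The exact 95% interval for 8/40 is 9.1% to 35.6%, so its arms are 10.9 and 15.6 points. For 6/40 it is 5.7% to 29.8%. One standard error at 20% is √(0.2 × 0.8/40) = 6.3 points. Every shortfall in the table is within the interval's arms; the largest is about one standard error.

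**Heavier loss, and numbers at risk.** Suppose instead that time on treatment is exponential with median m months and observation runs one month longer, with a 20% risk and no deaths. With c = ln2/m and e per month (0.2231/12 = 0.0186), crude = 1 - exp(-e) + exp(-e) × e/(e+c) × [1 - exp(-11(e+c))]. The number at risk at 12 months is 40 × 0.8 × 2^(-11/m).

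| Median m | Lost by 12 months | Crude | Shortfall, points | At risk at 12 months, of 40 |
|---|---|---|---|---|
| 4 | 85% | 10.2% | 9.8 | 4.8 |
| 6 | 72% | 12.3% | 7.7 | 9.0 |
| 9 | 57% | 14.3% | 5.7 | 13.7 |

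The bias grows with loss, but so does the difficulty of estimating a 12-month risk by any method.

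**The case against.** A reader might infer that 8.1 and 8.3 contradict each other, one being time-to-event and the other binary. The text does not support that. Section 8.1 carries the binary sentence too, the examples in 8.3 are introduced non-exclusively, and a count beside a Kaplan-Meier curve is ordinary reporting. What remains is that no main estimate is named.

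A reader might also infer that the plan scores patients lost early as free of AML and fibrosis. The sentence on binary endpoints sets no such rule. The sentence after it concerns clinical response, and its reach to these endpoints is unclear.

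It can be said that the crude proportion correctly describes incidence over the period actually observed, and is biased only against a fixed-time risk that the plan never names. That is fair, but the observed period differs between patients and depends on why they stop, so the proportion is hard to interpret or to compare with other data.

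The size is assumed, and exit is modelled as independent of the event. Section 5.3 calls for a marrow at the end of treatment, so transformation present at exit should be found. Exit for progression or lack of benefit may also make censoring informative, which no estimator here repairs. Finally, these are descriptive secondary endpoints with no test or stopping rule attached. All of this stands, and it limits the point to a needed specification.

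**Conclusion.** The plan holds two unreconciled estimates for each endpoint, and neither is safe as written if it is read as a risk by a fixed time. The crude proportion is low if patients are lost event-free. Kaplan-Meier is high if deaths without the event are censored.

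The stronger statement, that the plan understates both risks, goes too far: the direction depends on event-free loss, and the documents give no dropout figure. At an assumed 20% risk by 12 months, the shortfall is about 2 to 7 points for 20-60% loss and zero with none. A shortfall near 10 points needs about 85% loss, for which the documents give no basis. Within the 20-60% range the bias is smaller than the sampling error at n=40, but it is systematic and the exact interval does not reflect it.

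The change is worth making because it is cheap. ORR, the sample size and the stopping rules are not affected.

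**What to change.** In 8.1 and 8.3, for both AML transformation and marrow fibrosis:

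- Name as the main estimate the cumulative incidence from first dose, with death without the event as a competing event, and its 95% CI.
- Report it at a time fixed in advance, chosen so that adequate numbers remain at risk, and show the number at risk. Twelve months may be too late, as the second table shows.
- State the censoring rule.
- State that the 8.3 sentence on leaving before a clinical response applies to response endpoints only.
- Keep the raw n/N and person-time as description, without presenting the exact binomial interval as the interval for the risk.

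The cost is SAP wording and slightly more analysis; the event dates are already needed for the 8.1 curves. Reported risks may be somewhat higher than the crude rate. Possibly informative censoring remains and should be acknowledged when the results are reported.

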#### 4.7. Supportive Care Guidelines

4.7.1. Supportive measures including blood and platelet transfusions, antimicrobials, and analgesics are permitted.

4.7.2. The administration of anticancer therapies, other investigational cytotoxic agents, or prophylactic use of hematopoietic colony stimulating factors are not permitted.

4.7.3. Erythropoietin or hematopoietic colony stimulating factors for treatment of cytopenias are **discouraged**. If administered, the subject will not be eligible for a HI response assessment within one week of the receipt of Procrit or Neupogen, or for one month after receipt of Neulasta or Darbopoetin.

4.7.4. Platelet Transfusions: Platelet transfusion data must be captured on the case report form during the screening, treatment and extension periods. A unit of platelets is

defined as a single unit of platelet-rich plasma or buffy-coat concentrate or 1 apheresis (single donor) concentrate. The number of units transfused must be recorded.

ASCO guidelines suggest platelet transfusion criteria of:

- Platelet count <  $10 \times 10^9/L$  (i.e. severe thrombocytopenia)
- Signs of hemorrhage
- Subject with a high fever and platelet count <  $20 \times 10^9/L$
- Subject has a hyperleukocytosis
- There has been a rapid fall in platelet count and transfusions will not be readily available in case of emergencies

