### 6.2. Study Endpoints

**6.2.1. Primary Efficacy Endpoint:** The overall response rate (CR + PR + HI) based on the IWG-2006 criteria detailed below. Responses must last at least 4 weeks per definition.

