#### Complete Remission:

- Bone marrow:  $\leq 5\%$  myeloblasts with normal maturation of all cell lines
- Persistent dysplasia will be noted
- Peripheral blood
  - o Hemoglobin  $\geq 11\text{g/dL}$
  - o Platelets  $\geq 100 \times 10^9/\text{L}$

- Neutrophils  $\geq 1.0 \times 10^9/L$
- Blasts 0%

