**Failure:**

- Death during treatment or disease progression characterized by worsening of cytopenias or significant increase in percentage of bone marrow blasts

**Hematologic Improvement (HI) Response Criteria\*:** responses must last at least 8 weeks

- **Erythroid response** (if pretreatment hemoglobin  $< 11g/dL$ )
  - Hemoglobin increase by  $\geq 1.5g/dL$
  - Relevant reduction of units of RBC transfusions by an absolute number of at least 4 RBC transfusions/8 wk compared with the pretreatment transfusion number in the previous 8 wks. Only RBC transfusions given for a Hgb of  $\leq 9.0 g/dL$  pretreatment will count in the RBC transfusion response evaluation
- **Platelet response** (if pretreatment platelets  $< 100 \times 10^9/L$ )
  - Absolute increase of  $\geq 30 \times 10^9/L$  for patients starting with  $> 20 \times 10^9/L$  platelets
  - Increase from  $< 20 \times 10^9/L$  to  $> 20 \times 10^9/L$  and by at least 100%
- **Neutrophil response** (if pretreatment  $< 1.0 \times 10^9/L$ )
  - At least 100% increase and an absolute increase of  $> 0.5 \times 10^9/L$

\*Pretreatment counts averages of at least 2 measurements (not influenced by transfusions) for at least one week

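### The haemoglobin criteria for HI-erythroid and CR/PR do not require a period free of red-cell transfusion, and the 7-day exclusion is too short to keep carry-over out of the primary ORR

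*Combined protocol and SAP*

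**What the plan says.** Section 8: "The primary endpoint is the overall response rate (ORR) based on the IWG-2006 criteria", counting CR, PR and HI. The same count drives the futility rule.

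Section 6.2.1 sets the haemoglobin conditions:
- HI-erythroid (pretreatment haemoglobin below 11 g/dL) lists a rise of at least 1.5 g/dL, and a cut of at least 4 red-cell transfusions per 8 weeks. For HI, "responses must last at least 8 weeks".
- CR needs haemoglobin of at least 11 g/dL together with marrow, platelet, neutrophil and blast conditions. PR takes over the CR criteria that were abnormal before treatment, except for marrow blasts.
- For the primary endpoint as a whole, "Responses must last at least 4 weeks per definition".

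Transfusion enters in four places:
- Section 4.7.1: "Supportive measures including blood and platelet transfusions, antimicrobials, and analgesics are permitted". No red-cell trigger is given.
- The HI footnote, for baseline only: "Pretreatment counts averages of at least 2 measurements (not influenced by transfusions) for at least one week".
- Section 8.3, for on-study values: "Hemoglobin levels and platelet counts collected from patients that have received a transfusion within the last 7 days will not be considered". One window serves both counts, whichever product was given.
- Transfusion dependence ends an HI, is relapse after CR or PR, and is a disease-progression criterion. It is never defined by units or interval.

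**The concern.** A 7-day exclusion makes haemoglobin usable again from day 8, when most transfused red cells are still circulating. No sentence says that a transfusion inside the 4 or 8 weeks prevents or interrupts a response. The value is set aside and the clock is not said to stop.

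The protocol elsewhere matches its exclusion to how long an agent acts. Section 4.7.3 bars HI assessment for one week after short-acting growth factors and for one month after long-acting ones. Section 4.8.3.2 specifies an un-transfused platelet count for dose adjustment. The response criteria have no equivalent for on-treatment haemoglobin.

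At stake is the only primary endpoint of a single-arm trial. Supported haemoglobin scored as response moves the ORR in one direction, and there is no control arm in which the same error would cancel.

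**Working it through.** **Plan's own figures.** With the beta(1.2, 0.8) prior, the posterior after x responses in n patients is beta(1.2 + x, 0.8 + n − x), and the rule stops if Pr(p < 0.6) > 0.95. This gives 0.962 at 3/10 and 0.878 at 4/10; 0.957 at 8/20 and 0.901 at 9/20; 0.963 at 13/30 and 0.922 at 14/30. Table 1 is reproduced. Exact binomial recursion over the three looks gives stopping probabilities 0.971, 0.775, 0.391, 0.105 and 0.015 at true ORR 0.3 to 0.7, as in Table 2. The design figures are sound. The question is what is counted as a response.

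**Assumptions not in the documents.** 1 g/dL per unit, linear loss of transfused cells over T = 60, 90 or 110 days, and own production unchanged from baseline.

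**One 2-unit transfusion.** Increment on day d = 2 × (1 − d/T); it falls below 1.5 after day T/4.

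| T | day 8 | day 28 | day 56 | below 1.5 after day |
|---|---|---|---|---|
| 60 | 1.73 | 1.07 | 0.13 | 15 |
| 90 | 1.82 | 1.38 | 0.76 | 22.5 |
| 110 | 1.85 | 1.49 | 0.98 | 27.5 |

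Day 8 is outside the exclusion window and above the HI-erythroid threshold, but the increment does not last 8 weeks. Three units at T = 110 leave 3 × (1 − 56/110) = 1.47 on day 56, also short. For CR, the day-28 increment of 1.07 to 1.49 g/dL is enough to hold a patient near 11 g/dL.

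**Repeated 2-unit transfusions.** The value just before the next transfusion is more than 7 days after the last, so it is evaluable. It equals the sum of 2 × (1 − age/T) over all earlier transfusions still circulating.

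| Gap | T | end of 1st interval | end of 2nd | steady state |
|---|---|---|---|---|
| 21 d | 60 | 1.30 | 1.90 | 1.90 |
| 21 d | 90 | 1.53 | 2.60 | 3.33 |
| 21 d | 110 | 1.62 | 2.85 | 4.27 |
| 28 d | 60 | 1.07 | 1.20 | 1.20 |
| 28 d | 90 | 1.38 | 2.13 | 2.27 |
| 28 d | 110 | 1.49 | 2.47 | 2.95 |

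From the second interval, the 1.5 g/dL criterion is met at every evaluable point in five of the six cases. At the 28-day gap this period starts on day 28 + 8 = 36 and reaches 8 weeks on day 36 + 56 = 92, inside the four 28-day cycles (112 days) if the first transfusion comes early.

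**If HI were read with the 4-week duration.** Three units leave 3 × (1 − 36/T) = 1.2, 1.8 or 2.0 g/dL on day 36. Days 8 to 36 would then qualify from one transfusion in two of the three cases, so the two stated durations matter here.

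**Effect on the futility rule, illustration only.** Let m be an assumed share of true non-responders scored as responders, so observed ORR = p + (1 − p)m. The documents give no value for m.

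| True ORR | m = 0 | 5% | 10% | 20% |
|---|---|---|---|---|
| 0.40 | 0.775 | 0.669 | 0.550 | 0.317 |
| 0.50 | 0.391 | 0.299 | 0.220 | 0.105 |

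Entries are probabilities of a futility stop. One patient is enough to change a look: 3/10 stops and 4/10 continues.

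**The case against.** Several points on the other side stand and limit the conclusion.

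- A reader might infer that deletion leaves the higher values. It does the reverse: values in the week after a transfusion are the highest, and the pre-transfusion low remains evaluable. A deleted value cannot itself support a response, and under 4.1.1 a treated patient without qualifying values stays in the analysis. What remains is that deletion does not mark the transfusion as an interruption.
- A reader might infer that one transfusion produces HI-erythroid. Under the 8-week rule it does not.
- A reader might infer that any patient who worsens on decitabine and starts transfusion becomes a responder. If own production falls, the net rise is the increment minus the fall, and the calculation above assumes no fall. The case that survives is a patient who enters with low untransfused haemoglobin and is then kept well above it. For illustration, if red cells were given at 9.0 g/dL, the level 6.2.1 uses for counting pretreatment transfusions, a baseline of 9.0 − 1.5 = 7.5 g/dL or lower would suffice.
- The steady-state figures build up slowly: +4.27 needs five transfusions and 105 days. The first-interval values are the ones that apply early.
- Transfusion dependence, or a haemoglobin fall of 1.5 g/dL or more, ends HI, CR or PR. Two units every 21 days is 2 × 56/21 = 5.3 units per 8 weeks, above the protocol's 4-unit yardstick, so an assessor might call it dependence. The term is undefined, so this is not a dependable safeguard.
- In patients transfused before entry, the one-week baseline condition carries similar residue and offsets part of the effect. It offers nothing for patients first transfused on study.
- CR has other demanding conditions, and entry requires platelets of 100 × 10⁹/L or less, so some affected patients would already count through HI-platelet. For them the category changes and the ORR does not.
- Weekly blood counts make a missed low value less likely, but 5.2 requires them only until counts are stable and after eltrombopag dose changes.

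**Conclusion.** The gap is real. As written, haemoglobin supported by red-cell transfusion can count towards HI-erythroid through repeated transfusion above a low untransfused baseline, and towards CR or PR in a patient near 11 g/dL. The effect on ORR is upward, and it makes a futility stop less likely.

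The size cannot be derived from the documents. The carry-over figures rest on the assumed increment, red-cell life, transfusion pattern and unchanged own production, and the futility table rests on an assumed misclassification share. Neither estimates what will happen in this trial. A reader might infer that the reported ORR will be materially inflated; the documents do not support that. This is a cheap improvement worth making because the error runs one way, there is no control arm, and a single patient can change a futility decision.

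**What to change.** In 6.2.1 and 8.3, state that:
- the haemoglobin arm of HI-erythroid requires no red-cell transfusion during its 8-week response period, and patients transfused in that period can qualify for HI-erythroid only through the reduction of at least 4 units per 8 weeks;
- the CR/PR haemoglobin condition requires no red-cell transfusion during the 4-week confirmation period;
- a red-cell transfusion in the period interrupts the response for these criteria, and does not merely remove a value.

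Keep the 7-day window as a filter on single values. Define transfusion dependence by units and interval. Reconcile the 4-week duration stated for the primary endpoint with the 8 weeks stated for HI. Record red-cell transfusion dates and units explicitly: 4.7.4 requires case report form capture and unit counts for platelets only, although 5.2 assesses transfusions at every visit.

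These changes concern how response is scored; transfusion practice is unaffected. The cost is wording and a small addition to data capture, and the observed ORR may be slightly lower.

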## 5.2 On-Study Procedures

PROCEDURES	Pre-Study Screen o	Cycle 1 Day 1	Cycle 1 Day 8 (+/- 2 days)	Cycle 1 Day 15 (+/- 2 days)	Cycle 1 Day 22 (+/- 2 days)	Day 1 Cycle 2 onwards (+/- 5 days)	End of Treatment Visit (+/- 5 days)	Safety Visit 28 days after last dose (+/- 28 days)
Informed Consent	X							
Eligibility	X	X						
Medical History	X							
Patient Weight	X							
Vital Signs	X	X	X	X	X	X	X	X
Physical Exam and Performance Status	X	X				X	X	X
Concomitant Medications	X	X	X	X	X	X	X	X
Transfusion and Supportive Care Assessment	X	X	X	X	X	X	X	X
CBC with differential	X*	X	X	X	X	X 	X	X 
Blood Chemistries (AST, ALT, bilirubin)	X** a	X	X	X	X	X 	X	X
12-lead EKG	X a							
Bone marrow aspiration and/or biopsy	X					X 	X	
IPSS score & WHO disease classification	X					X 	X	
Pregnancy Test	X†							
Investigational Drug Dispense		X				X		
AE and SAE assessment	X	X	X	X	X	X	X	X
Optional: Correlative studies 	X							

oScreening must be performed within 4 weeks prior to study drug initiation / study start unless otherwise indicated

\*CBC with differential and blood chemistries including iron studies (sodium, potassium, BUN, creatinine, glucose, calcium, phosphate, magnesium, AST, ALT, total bilirubin, alkaline phosphate, uric acid, serum iron, transferrin, transferrin saturation, total iron binding capacity and ferritin) must be performed within 72 hours of Cycle 1 Day 1

^Serum iron, transferrin, transferrin saturation, total iron binding capacity and ferritin are required only on Cycle 1 Day 1 and do not need to be repeated

aEKG, including QTc intervals, at screening or baseline. A follow-up EKG will be performed if a subject experiences a clinically relevant abnormality.

†Within 7 days of Day 1 in females of child-bearing potential

Weekly CBC with differential and blood chemistries required until stable counts, and weekly x4 weeks after any change in eltrombopag dosing

Weekly CBC with differential should be performed weekly for the 4 weeks after discontinuation of eltrombopag

Bone marrow aspiration and/or biopsy with cytogenetics required for study entry, and every cycle for the first 4 cycles for primary outcome, and then every 3 cycles as clinically indicated. Cytogenetics do not need to be repeated if normal at study start.

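### Section 8.3 voids hemoglobin and platelet values for 7 days after a transfusion without naming the component, so as written red cells remove valid platelet counts and platelet transfusions remove valid hemoglobin values

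*Combined protocol and SAP*

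**What the plan says.** Section 8.3 sets one trigger for two measurements: "Hemoglobin levels and platelet counts collected from patients that have received a transfusion within the last 7 days will not be considered" in the analysis. The sentence neither names the blood component nor pairs a component with a measurement.

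Both kinds of transfusion occur on study. Section 4.7.1 says: "Supportive measures including blood and platelet transfusions, antimicrobials, and analgesics are permitted". Elsewhere the protocol names the component when it means one. The erythroid criterion in Section 6.2.1 begins a condition with "Only RBC transfusions given for a Hgb of", and Section 4.7.4 is specific to platelets.

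Section 6.2.1 counts hematologic improvement (HI) in the ORR and requires of it that "responses must last at least 8 weeks". Its footnote on baseline values reads "Pretreatment counts averages of at least 2 measurements (not influenced by transfusions) for at least one week". After cycle 1, footnote 1 of the Section 5.2 schedule has "Weekly CBC with differential and blood chemistries required until stable counts", and again for four weeks after an eltrombopag dose change. Otherwise the scheduled count is on Day 1 of each cycle.

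No section says how to score a patient who has too few usable counts left.

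**The concern.** The purpose of such a rule is to stop transfused cells from passing as response. Red cells do not raise the platelet count, and platelets do not raise hemoglobin. A rule that lets either product void both values therefore discards data it has no reason to discard.

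The HI-platelet component is the most exposed. Entry requires platelets at or below 100 x 10^9/L, so nearly every patient can be assessed for it, and it is the response most directly tied to eltrombopag. A patient whose platelets rise while red cells are still needed is a plausible single-lineage responder, and the literal rule masks that patient's platelet counts. The mirror case is a hemoglobin rise in a patient still receiving platelets. At stake are the primary ORR, the responder counts at the futility looks, and the platelet response and durable platelet response endpoints.

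**Working it through.** **Plan's own figures first.** Section 8 attaches no number to the 7-day rule, so the check starts with the futility design for the affected endpoint. With prior beta(1.2, 0.8), stop if Pr(p < 0.6) > 0.95 under beta(1.2 + x, 0.8 + n - x). This gives 0-3 of 10, 0-8 of 20 and 0-13 of 30, as in Table 1. Exact binomial recursion over the three looks gives stopping probabilities of 0.9705, 0.7749, 0.3906, 0.1054 and 0.0147 at true ORRs of 0.3 to 0.7. Table 2 has 0.971, 0.775, 0.391, 0.105 and 0.015. The design reproduces.

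**Inputs for the rule.**
- Void window: 7 days (Section 8.3).
- Primary window: four 28-day cycles, 4 x 28 = 112 days (Sections 4.1 and 8).
- HI duration: 8 weeks = 56 days (Section 6.2.1).
- Red-cell interval: not in the documents; assumed 7 to 28 days.

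**Weekly counts.** Share of platelet counts voided by red cells = min(1, 7/interval), averaged over the timing of transfusions, with day 7 inside the window and a same-day count taken as drawn before the transfusion.

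| Red-cell interval (days) | Voided as written | Voided if component-specific |
|---|---|---|
| 7 | 7/7 = 100% | 0% |
| 10 | 7/10 = 70% | 0% |
| 14 | 7/14 = 50% | 0% |
| 21 | 7/21 = 33% | 0% |
| 28 | 7/28 = 25% | 0% |

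At 14 days and longer, the longest gap between usable counts is 14 days.

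If day 7 falls outside the window, the average losses at 7, 14 and 28 days drop to 86%, 43% and 21%. At some alignments nothing is lost, for example when each count is drawn just before a weekly transfusion.

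**A load the protocol itself contemplates.** The erythroid transfusion criterion requires a reduction of "at least 4 RBC transfusions/8 wk compared with the pretreatment transfusion number in the previous 8 wks". Four transfusions on evenly spaced days mask 4 x 7 = 28 of 56 days (50%). Given on two days, they mask 2 x 7 = 14 of 56 (25%).

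**Weekly in cycle 1, then Day 1 only** (days 8, 15, 22, 29, 57, 85, 113). Average losses are unchanged, but gaps between usable counts reach 91 days at a 10-day interval and 56 days at a 21-day interval. Timing matters even when red cells are infrequent. With red cells on days 24, 52, 80 and 108, the counts on days 29, 57, 85 and 113 each fall 5 days after a transfusion. All four are void, leaving days 8, 15 and 22. These span 14 days and cannot confirm 56.

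**Sensitivity of the design, not an estimate.** If 5, 10 or 15 points of a true 60% ORR became unscorable and counted as non-response, the probability of a futility stop would rise from 0.105 to 0.220, 0.391 or 0.591. Five points is 0.05 x 40 = 2 patients.

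**The case against.** The sentence may have been meant as a pairing, hemoglobin with red cells and platelets with platelet transfusions. The baseline footnote, which speaks of counts not influenced by transfusion, points to that purpose. The pairing is not written, however, and two analysts could apply the sentence differently and reach different ORRs. If pairing was intended, the fix merely states it.

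Several limits on the point do stand.
- Losses are partial at intervals of 14 days or more with weekly counts. A patient still needing red cells may also not count as stable, so weekly sampling could continue; the schedule does not define stable.
- Other routes to response survive. HI-neutrophil is untouched, and the red-cell reduction route counts transfusions rather than hemoglobin values. Exposure is confined mainly to patients whose only response is HI in one lineage.
- Complete remission needs hemoglobin of at least 11 g/dL, and partial remission carries the blood criteria over if they were abnormal before treatment. A component-specific rule would still void hemoglobin after red cells, so it does little for these categories in red-cell-dependent patients.
- The baseline footnote does not share the defect. A platelet count after red cells is not influenced by them and stays usable.
- The direction is not fixed. Dropped counts could include low values showing that a response was lost within 8 weeks, which would err upward.

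**Conclusion.** The point holds as a defect of wording with consequences for the primary endpoint. As written, the exclusion is not component-specific, nothing elsewhere corrects it, and it discards valid values.

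A reader might infer that red-cell-dependent patients cannot be scored for platelet response at all. The documents do not support that. With weekly counts, total loss arises only at about weekly red cells, and then depends on how day 7 is counted.

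A reader might also convert the rule into ORR points. Assuming 4 to 8 of 40 patients on red cells every 1 to 2 weeks, 40% of them platelet responders, gives 4 x 0.4/40 = 4% to 8 x 0.4/40 = 8%. None of those inputs is in the documents. The sum also treats patients who keep half their counts as wholly lost, and ignores other routes to response. The effect on ORR is therefore unknown.

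Nor is a definite downward bias shown, because no section says how sparse counts are scored. Downward is the likelier direction.

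**What to change.** Replace the sentence in Section 8.3 with: *Platelet counts collected within 7 days after a platelet transfusion, and hemoglobin values collected within 7 days after a red-cell transfusion, are excluded from the analysis.* State whether day 7 itself is inside the window.

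Add one sentence on how a patient with too few usable counts to confirm 8 weeks is scored. Counting such a patient as a non-responder, and reporting how many there are, would fit the way Section 8 treats early toxicity dropouts. No change to the baseline footnote in Section 6.2.1 is needed.

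The cost is two sentences of text, plus matching transfusion type and date to each blood count, including transfusions given outside the center. Section 5.2 already assesses transfusions at every visit, Section 4.7.4 already requires platelet transfusion data on the case report form, and the erythroid criterion already needs red-cell transfusion counts. No clinical rule changes.
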